4.6.2. Adverse Events of Special Interest

AESIs are AEs (serious or non-serious) required to be monitored, documented, and managed in a pre-specified manner as described in the protocol. In this study, AESI are listed below (as provided in the protocol):

- Grade ≥ 2 infusion-related reactions to REGN10933+REGN10987 through day 4
- Grade ≥ 3 injection-site reactions to REGN10933+REGN10987 or each dose of Moderna mRNA-1273 vaccine through day 4 post-injection
- Grade ≥ 2 hypersensitivity reactions to REGN10933+REGN10987 or each dose of Moderna mRNA-1273 vaccine through day 29 post-infusion or post-injection (as applicable)

4.6.3. Laboratory Safety Variables

The clinical laboratory data consists of blood chemistry, hematology, and urinalysis.

Samples for laboratory testing will be collected at visits according to the Schedule of Events (Appendix 11.1). Samples will be analyzed by a central laboratory. The clinical laboratory data consists of blood chemistry, hematology, urinalysis and other specified in section 9.2.5 of the protocol.

Clinical laboratory values will be presented in Standard International (SI) units.

Potentially clinically significant value (PCSV) ranges will be applied to the laboratory test values as applicable (see PCSV criteria in Appendix 11.2).

4.6.4. Vital Signs

Vital signs collected include temperature, blood pressure, heart rate, and respiratory rate. PCSV ranges will be applied to corresponding vital sign parameter values according to (see PCSV criteria in Appendix 11.2).

4.6.5. SARS-CoV-2 test results

SARS-CoV-2 rapid RT-PCR testing will be conducted using nasopharyngeal swabs throughout the study according to the specific Schedules of Events for each enrolment wave.

SARS-CoV-2 rapid RT-PCR will be performed at unscheduled or planned scheduled visits for subjects with signs or symptoms consistent with COVID-19 or those who obtain a positive SARS-CoV-2 RT-PCR test result from the study site or another testing location.

4.7. Pharmacokinetic Variables

The pharmacokinetic variables are the concentrations of REGN10933 and REGN10987 in serum and time when a sample was collected.

4.8. Immunogenicity Variables

The immunogenicity variables are ADA response status, titer, and NAb status at nominal sampling time/visit. Serum samples for immunogenicity analysis will be collected at the timepoints outlined in the Schedule of Events (Appendix 11.1). Samples positive in the ADA assays will be further characterized for ADA titers and for the presence of NAb.

5. STATISTICAL METHODS

For continuous variables, descriptive statistics will include the following: the number of subjects reflected in the calculation (n), mean, median, standard deviation, minimum, and maximum. For categorical or ordinal data, frequencies and percentages will be displayed for each category.

5.1. Demographics and Baseline Characteristics

Demographic and baseline characteristics will be tabulated by treatment group and overall for the PPS, mFAS and SAF analysis sets.

Baseline is defined as the last available value prior to the first dose of Moderna mRNA-1273 vaccine or REGN10933+REGN10987 (as applicable and whichever occurs first).

5.2. Medical History

Medical history will be tabulated by SOC and PT and by treatment group and overall for the SAF.

5.3. Prior/Concomitant Medications & Procedures

Prior medications and procedures will be tabulated by treatment group for the SAF.

Concomitant medications will be tabulated by treatment group for the entire study period for the SAF.

5.4. Prohibited Medications

Prohibited medications will be tabulated by treatment group for the SAF.

5.5. Subject Disposition

Subject counts within each analysis set by treatment group and total will be presented. Additionally, the following will be tabulated:

- Total number of screened subjects [defined as who signed the Informed Consent Form (ICF)]
- Number of randomized subjects and number and reasons for subjects not randomized.
- Number of subjects who discontinued from the study along with reason for study discontinuation

If applicable, a listing of subjects treated but not randomized, subjects randomized but not treated, and subjects randomized but not treated as randomized will be provided.

5.6. Extent of Study Treatment Exposure and Compliance

The number of subjects whose infusion of REGN10933+REGN10987 or whose injection of vaccine was interrupted or incomplete will be tabulated by treatment group for the SAF.

The number of injections of primary series vaccine will be tabulated by treatment group for the SAF. Among those with more than one injection of vaccine, the time between first and second vaccination will be tabulated by treatment group for the SAF. The number of subjects with injections of booster vaccine will be tabulated by treatment group. Time from second injection of primary series vaccine to booster vaccine injection will be tabulated by treatment group for the SAF.

The extent of follow-up (completing visit 56 days after the first vaccine dose, visit 52 weeks after the first vaccine dose) will be tabulated by treatment group for the SAF.

5.7. Analysis of Vaccine Response Variables

For efficacy variables, baseline is defined as the last available value prior to the first dose of Moderna mRNA-1273 vaccine. The analyses will be conducted based on the observed data with no imputation for missing data. Values below the LLOQ will be set to half of LLOQ and values above the upper limit of quantification (ULOQ) will be set to the ULOQ.

5.7.1. Analysis of Primary Vaccine Response Variable

The primary endpoint is the 50% inhibitory dilution (ID_{50}) neutralizing antibody titers of vaccine-induced neutralizing antibodies to SARS-CoV-2, assessed on 56 days after the first dose of the vaccine. The 56-day time point corresponds to study day 71 for study arms 1, 2, 3, 7, 8, 6a, and 6c, and study day 57 for study arms 4, 5, 9, 6b, and 6d. For all analyses, the vaccine alone arms (i.e. arms 6a, 6b, 6c and 6d) will be pooled in the analysis.

An analysis of covariance (ANCOVA) model with treatment group as a fixed effect and age as a continuous covariate will be run in order to perform the primary analysis for the PPS. The least squares mean estimates and associated 95% confidence interval for the endpoint will be reported for each treatment group, as well as for the relative differences between each combination of Moderna mRNA-1273 vaccine and REGN10933+REGN10987 arm (i.e. arms 1 - 5, and 7 - 9) and the pooled vaccine alone group.

Data may be fitted in the log 2 scale, and final outputs of geometric means and relative differences of the geometric mean ratio will be reported through the back-transformation.

Let $\hat{\mu}_A$, $\hat{\mu}_B$ denote the least squares mean estimates and $\hat{\sigma}_A^2$, $\hat{\sigma}_B^2$, $\hat{\sigma}_{AB}$ denote the associated estimated variances and covariance for the endpoint of interest of treatment groups A and B, respectively.

Geometric means and associated 95% confidence intervals for treatment groups A and B will be calculated as:

$$2^{\hat{\mu}_A}, (2^{\hat{\mu}_A - t_{df,\alpha} \times \hat{\sigma}_A}, 2^{\hat{\mu}_A + t_{df,\alpha} \times \hat{\sigma}_A}),$$

and

$$2^{\hat{\mu}_B}, (2^{\hat{\mu}_B - t_{df,\alpha} \times \hat{\sigma}_B}, 2^{\hat{\mu}_B + t_{df,\alpha} \times \hat{\sigma}_B}).$$

Relative difference of the geometric mean ratio and associated 95% confidence interval for treatment groups A and B will be calculated as:

$$(2^{\widehat{\mu}_A - \widehat{\mu}_B} - 1) \times 100\%, \left(2^{\frac{(\widehat{\mu}_A - \widehat{\mu}_B) - t_{df, \alpha} \times \sqrt{\widehat{\sigma}_A^2 - 2\widehat{\sigma}_{AB} + \widehat{\sigma}_B^2}}{2} - 1} \right) \times 100\%, \left(2^{\frac{(\widehat{\mu}_A - \widehat{\mu}_B) + t_{df, \alpha} \times \sqrt{\widehat{\sigma}_A^2 - 2\widehat{\sigma}_{AB} + \widehat{\sigma}_B^2}}{2} - 1} \right) \times 100\%.$$

5.7.2. Analysis of Secondary Vaccine Response Variables

Secondary vaccine response variables will also be analyzed using an ANCOVA model with treatment group as a fixed effect and age as a covariate in the model using the Per Protocol Analysis Set.

The least square means estimates as well as the relative difference of these estimates between each combination of Moderna mRNA-1273 vaccine and REGN10933+REGN10987 group and the pooled vaccine alone group will be provided along with the associated 95% confidence interval.

Data may be fitted in the log scale, and final outputs will be back-transformed to the original scale using the same method as described for the primary endpoint (see Section 5.7.1).

For concentrations of vaccine-induced antibodies to the following SARS-CoV-2 antigens, if a log transformation is needed, modelling will use a log transformation with base 10:

- Anti-S protein
- Anti-RBD
- Other S protein subdomains (including S1, S2, and NTD)

For variables listed below, if a log transformation is needed, modelling will use a log transformation with base 2:

- 50% inhibitory dilution (ID₅₀) titers of vaccine-induced neutralizing antibodies to SARS-CoV-2 S protein assessed over time after the first dose of Moderna mRNA-1273 vaccine

Numerical summaries of observed value, change from baseline, and percentage change from baseline will also be tabulated.

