1. INTRODUCTION

Severe acute respiratory syndrome coronavirus 2 (SARS-CoV-2) is a novel RNA betacoronavirus, initially identified in patients experiencing atypical pneumonia in Wuhan City, China (Zhu, 2020) and later identified as the causative pathogen of coronavirus disease 2019 (COVID-19) (WHO, 2020).

Coronaviruses consist of an RNA genome packaged in nucleocapsid (N) protein. The resulting capsid is surrounded by an outer envelope comprised of membrane (M) protein and envelope (E) protein, which are involved in virus assembly, and spike (S) protein, which mediates entry into host cells. The S protein is essential for virus infectivity and is the main target of the humoral immune response, as demonstrated by serology analysis of recovered COVID-19 patients (Long, 2020). By mediating binding to the host receptor angiotensin-converting enzyme 2 (ACE2), the S protein facilitates membrane fusion and entry of the virus into susceptible cells (Hoffmann, 2020). The S protein is itself composed of 2 functional subunits: the S1 subunit, which contains the receptor binding domain (RBD) responsible for binding to ACE2 on host cells, and the S2 subunit, which mediates fusion of the viral and cellular membranes (Walls, 2020).

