2.2. Secondary Objectives

The secondary objectives of the study are:

- To quantify the alteration of antigen specificity of vaccine-induced SARS-CoV-2 antibody responses when administered with different dose regimens of REGN10933+REGN10987
- To evaluate the safety and tolerability of REGN10933+REGN10987 and Moderna mRNA-1273 vaccine when administered in close succession
- To assess the concentrations of REGN10933 and REGN10987 in serum over time in subjects who receive REGN10933+REGN10987 and Moderna mRNA-1273 vaccine
- To evaluate the immunogenicity of REGN10933 and REGN10987 over time

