4.2. Secondary Endpoints

The secondary endpoints are:

- Absolute values, change from baseline, and percentage change from baseline in concentrations of vaccine-induced antibodies to the following SARS-CoV-2 antigens over time:
 - Anti-S protein
 - Anti-RBD
 - Other S protein subdomains (including S1, S2, and NTD)
- 50% inhibitory dilution (ID_{50}) titers of vaccine-induced neutralizing antibodies to SARS-CoV-2 S protein assessed over time after the first dose of Moderna mRNA-1273 vaccine

- Proportion of subjects with treatment-emergent adverse events (TEAEs) throughout the study
- Proportion of subjects with treatment-emergent serious adverse events (SAEs) throughout the study
- Proportion of subjects with infusion-related reactions (grade ≥ 2) to REGN10933+REGN10987 through day 4 post-infusion
- Proportion of subjects with injection site reactions (grade ≥ 3) to REGN10933+REGN10987 or each dose of Moderna mRNA-1273 vaccine through day 4 post-injection
- Proportion of subjects with hypersensitivity reactions (grade ≥ 2) to REGN10933+REGN10987 or each dose of Moderna mRNA-1273 vaccine through day 29 post-infusion or post-injection (as applicable)
- Concentrations of REGN10933 and REGN10987 in serum over time
- Immunogenicity, as measured by anti-drug antibodies (ADA) and neutralizing antibodies (NAb) to REGN10933 and REGN10987

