7. Note that not all subjects will receive study drug at randomization. Refer to Section 8.5 and Figure 1 for more information.

Study arms 4 and 5: Subjects assigned to study arms 4 and 5 will receive both the study drug and vaccine on day 1. The study drug will be administered first, followed by the vaccine. There must be a minimum of 2 hours waiting period between administration of the study drug and subsequent vaccine administration. Approximately 24 hours after completion of the study drug and vaccine administration on day 1, subjects will be followed up by telephone for safety. Subjects should be monitored for at least 1 hour after study drug or vaccine administration.

Study arms 6a, 6b, 6c, and 6d only: Subjects assigned to one of these study arms will not receive study drug. These subjects will receive the vaccine only. These subjects should be monitored for at least 30 minutes after vaccine administration.

Refer to Section 9.2.2 for additional information concerning administration and monitoring requirements following study drug and/or vaccine administration.

8. Serology characterization assays will be used to assess antibodies against various SARS-CoV-2 antigens including: S protein, RBD, S1, and N protein. Refer to Section 9.2.3.1, Section 9.2.3.2, and Section 9.2.3.3 for more information on procedures and assays related to vaccine response assessment.
9. Vital signs, including temperature, blood pressure, heart rate, and respiratory rate will be collected prior to and 30 minutes following each administration of the study drug or vaccine primary series (first and second dose) as described in Section 9.2.4.1.
10. Actual dosing time and drug concentration sample collection times will be recorded.

Study arms 1, 2, 3, 7, 8, and 9 (receiving IV infusion of study drug): At the indicated visit, blood for assessment of drug concentration in serum will be taken prior to dosing and within 60 minutes after the end of infusion (EOI). The EOI sample should be collected from the arm contralateral to that used for IV infusion. If not medically feasible, the EOI sample can be drawn from the same arm, but not from the infusion catheter.

Study arms 4 and 5 (receiving SC injection of study drug): At the screening/baseline visit, blood for assessment of drug concentration in serum will be taken prior to dosing. The post-dose blood collection should occur at least 1 hour after study drug administration.

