1.2.2. Secondary Objectives

The secondary objectives of the study are:

- To quantify the alteration of antigen specificity of vaccine-induced SARS-CoV-2 antibody responses when administered with different dose regimens of REGN10933+REGN10987
- To evaluate the safety and tolerability of REGN10933+REGN10987 and Moderna mRNA-1273 vaccine when administered in close succession
- To assess the concentrations of REGN10933 and REGN10987 in serum over time in subjects who receive REGN10933+REGN10987 and Moderna mRNA-1273 vaccine
- To evaluate the immunogenicity of REGN10933 and REGN10987 over time

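### The secondary objective is to quantify altered antigen specificity, but the planned analysis compares one antigen at a time with control, so the shift between antigens gets no estimate and no confidence interval

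*SAP*

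**What the plan says.** Protocol 2.2 sets the objective "To quantify the alteration of antigen specificity of vaccine-induced SARS-CoV-2 antibody responses" under different dose regimens, and SAP 1.2.2 repeats it. Protocol 3.2.1.6 gives the motive: exogenous antibodies might skew the response. Both antibodies bind the RBD (Protocol 1).

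The endpoint (Protocol 4.2) is the concentration of antibodies to S protein, to RBD, and to "Other S protein subdomains (including S1, S2, and NTD"). SAP 4.5.2 and 5.7.2 carry the same list.

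The analysis in SAP 5.7.2 is: "Secondary vaccine response variables will also be analyzed using an ANCOVA model with treatment group as a fixed effect". The model also adjusts for age. The output is "The least square means estimates as well as the relative difference of these estimates between each combination of Moderna mRNA-1273 vaccine and REGN10933+REGN10987 group". Each such arm is set against the combined vaccine-only arms with 95% intervals, and summaries of observed value, change and percentage change from baseline are added. SAP 5.7.3 to 5.7.5 add no comparison between antigens.

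The assay descriptions give different lists. Footnote 8 to the schedules (Protocol 9.1.1, repeated in SAP 11.1) reads: "Serology characterization assays will be used to assess antibodies against various SARS-CoV-2 antigens including: S protein, RBD, S1, and N protein". Protocol 9.2.3.2 names S trimer, RBD, S1 and nucleocapsid. Protocol 3.2.1.6 describes a kit for S trimer and S1 RBD. None names S2 or NTD.

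**The concern.** Specificity describes how a subject's response is spread across antigens. A lower anti-RBD level than control fits two different findings: a weaker response to all of spike with specificity unchanged, or a response steered away from the RBD. Telling them apart with stated uncertainty needs an estimate of the drug effect on RBD minus the drug effect on another part of spike. The plan defines no such quantity.

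Reading intervals side by side does not replace it. One antigen's interval may exclude no effect while another's includes it, and the two effects may still not differ. Without a named contrast, the antigen pair used to describe a shift can also be chosen after the results are seen.

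The difference between the lists matters because the comparison needs a part of spike without the RBD. Protocol 1 describes "the S1 subunit, which contains the receptor binding domain (RBD) responsible for binding to ACE2", with S2 as the other subunit. Whole S contains S1, and nucleocapsid is not part of spike. If only the antigens in the assay descriptions are measured, no RBD-free spike antigen is available.

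**Working it through.** **What the two patterns look like.** Suppose the drug halves antibody levels.

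| Case | RBD v control | S2 v control | Effect on log10(RBD/S2) |
|---|---|---|---|
| All of spike equally | −50% | −50% | log10(0.5/0.5) = 0 |
| RBD only | −50% | 0% | log10(0.5/1.0) = −0.301 |

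The planned tables would show the second and third columns. The fourth, with its interval, is not planned.

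**Why the interval cannot be recovered.** For two drug effects on the log scale, Var(difference) = V1 + V2 − 2·Cov. The separate models give V1 and V2. The covariance depends on the within-subject correlation rho between antigens, which no planned table reports.

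**The plan's own figure.** Protocol 11.2 gives SD 0.30 log10, for neutralizing ID50 only, and group sizes 30 and 46. Half-width = t(0.975, 74) × SD × √(1/30 + 1/46) = 1.9925 × 0.30 × 0.2347 = 0.140, which matches the stated 0.14.

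**Precision of a within-subject log ratio.** If both antigens have the same SD, the ratio's SD is SD × √(2(1 − rho)), so the half-width is 0.140 × √(2(1 − rho)) at SD 0.30. Neither the binding-antibody SD nor rho is in the documents. Both are assumed here, with SD 0.45 as the wider case.

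| rho | SD 0.30 | SD 0.45 |
|---|---|---|
| 0 | 0.198 | 0.298 |
| 0.5 | 0.140 | 0.210 |
| 0.8 | 0.089 | 0.133 |
| 0.9 | 0.063 | 0.094 |

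Using the residual degrees of freedom of the full ANCOVA (276) changes the SD 0.30 range only to 0.196–0.062.

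**Correlation needed for a half-width below 0.15.**
- SD 0.30: 2(1 − rho) < (0.15/0.1403)² = 1.143, so rho > 0.43.
- SD 0.45: 2(1 − rho) < (0.15/0.2104)² = 0.508, so rho > 0.75.

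A halving confined to the RBD (0.301) exceeds every half-width in the table, though only just at SD 0.45 with rho 0 (0.298).

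**If only RBD and whole S are available.** Assume that anti-RBD makes up a share f of the anti-S signal and that only the RBD part halves. Whole S then falls to 1 − f/2 of control, that is 0.85, 0.70 or 0.55 for f = 0.3, 0.6 or 0.9. The log10 RBD:S effect is log10(0.5/0.85) = −0.230, log10(0.5/0.70) = −0.146 or log10(0.5/0.55) = −0.041, against −0.301 for RBD:S2. The larger the RBD share, the less this ratio can show.

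**The case against.** SAP 5.7.2 itself lists S2 and NTD, and on the protocol's description S2 is free of the RBD. A reader who looked only at the assay descriptions might infer that the plan has no RBD-free antigen. The endpoint and analysis sections contradict that. Footnote 8 and Protocol 9.2.3.2 also introduce their lists with open wording ("including"), so they do not show that S2 and NTD will be left out. This part stands: the lists need reconciling, but nothing shows that an assay has been dropped.

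A reader might also infer that a specificity shift cannot be told from a weaker response. If S2 and NTD are run, the planned results would show a fall in RBD with S2 spared, so the pattern is visible. What is missing is its estimate and interval.

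Other planned work bears on specificity: antibodies competing with the drug's own epitopes (Protocol 2.3 and 5.2), possible epitope mapping (3.2.1.6 and 9.2.3.2), and B-cell responses by subdomain (4.3). All of it is exploratory or optional. The competition assay is not among the variables in SAP 4.5.3. None of it supplies the missing contrast.

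Finally, the study is descriptive, with no hypothesis testing (Protocol 11.1), and the ratio could be derived later from the same data. That limits the stakes, but a contrast derived later would not be pre-specified.

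**Conclusion.** The point holds in a limited form. A named secondary objective concerns the relation between antigens, and the planned analysis gives no estimate or interval for that relation. Reading per-antigen results side by side is the only route to it. In addition, the endpoint list and the assay descriptions disagree on S2 and NTD. If only the named assays were run, the RBD-free comparator would be lost.

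No general claim about precision is supported. It is tempting to say that the ratio would resolve a 0.15 log10 shift. At 30 v 46 that holds only if rho exceeds about 0.43 (SD 0.30) or about 0.75 (SD 0.45), and neither quantity is documented for binding antibodies. The case for the contrast does not depend on these figures: a uniform fall leaves the ratio unchanged and an RBD-only fall does not, whatever the SD.

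The primary endpoint and its analysis are unaffected. This is an inexpensive improvement to a secondary analysis.

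**What to change.** 1. In SAP 5.7.2, add as the variables that answer this objective the within-subject log10 ratios anti-RBD:anti-S2, anti-RBD:anti-NTD and anti-RBD:anti-S at 56 days after dose 1. Analyse them with the ANCOVA already planned, each drug arm against pooled vaccine alone, with 95% intervals.
2. Reconcile footnote 8 (protocol and SAP) and Protocol 3.2.1.6 and 9.2.3.2 with the endpoint list in Protocol 4.2. If S2 and NTD will not be run, state that specificity is assessed only as RBD relative to whole S.
3. Report, for each antigen, how many values were set to half the LLOQ or to the ULOQ.

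Cost: SAP wording, three derived variables and a few more descriptive contrasts. S2 and NTD are already named endpoints, so no sample or endpoint is added. The drawback is that the substitution rules in SAP 5.7 and 6.2 can distort a ratio when one antigen is at a limit and the other is not, which is why item 3 is needed.

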11.4.3. Analysis of Primary Vaccine Response Endpoint

The primary endpoint is the 50% inhibitory dilution (ID₅₀) titers of vaccine-induced neutralizing antibodies to SARS-CoV-2 pseudovirus, assessed on 56 days after the first dose of the vaccine (ie, the vaccine response assessment period). The 56-day time point corresponds to study day 71 for study arms 1, 2, 3, 7, 8, 6a, and 6c, and study day 57 for study arms 4, 5, 9, 6b, and 6d.

An analysis of covariance (ANCOVA) model with treatment group as a fixed effect and age as a covariate will be fit to the data as the primary analysis.

The least squares mean estimates for the endpoint will be presented for each treatment group, as well as for the differences between treatment groups. Associated 95% confidence intervals will also be reported for each treatment group and for between-group comparisons.

Data will be fitted in the log scale, and final outputs will be reported in geometric means and differences of the geometric means.

Accompanying descriptive analyses will also be provided. The analyses will be conducted based on the observed data with no imputation for missing data. Values below the limit of quantification (LOQ) will be set to half of LOQ.

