4.5.2. Secondary Vaccine Response Variables

The secondary vaccine response variables in this study include:

- Absolute values, change from baseline, and percentage change from baseline in concentrations of vaccine-induced antibodies to the following SARS-CoV-2 antigens over time:
 - Anti-S protein
 - Anti-RBD

- Other S protein subdomains (including S1, S2, and NTD)
- 50% inhibitory dilution (ID₅₀) neutralizing antibody titers of vaccine-induced neutralizing antibodies to SARS-CoV-2 S protein assessed over time after the first dose of Moderna mRNA 1273 vaccine

The time points of the secondary vaccine response variables include 0, 6, 14, 28, 42, 56 days after the first dose of Moderna mRNA 1273 vaccine, except that day 56 is not applicable to the variable of 50% inhibitory dilution (ID₅₀) titers of vaccine-induced neutralizing antibodies to SARS-CoV-2. In addition, variables associated with 6 days after the first dose of Moderna mRNA 1273 vaccine are only applicable to study arms 6d and 9, which corresponds to study day 7 for these two arms. Variables will be reported in both BAU/mL and AU/mL units.

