4.5.3. Exploratory Vaccine Response Variables

The exploratory vaccine response variables in this study include

- Absolute percentages, change, and percentage change from baseline of blood-derived memory T cell responses specific to SARS-CoV-2 viral peptides over time
- Absolute percentages, change, and percentage change from baseline of blood-derived B cell responses specific to SARS-CoV-2 S protein, RBD, and other S protein subdomains over time

The time points of the exploratory vaccine response variables include 0, 6, 14, 28, 42, 56 days after the first dose of Moderna mRNA 1273 vaccine. In addition, variables associated with 6 days after the first dose of Moderna mRNA 1273 vaccine are only applicable to study arms 6d and 9, which corresponds to study day 7 for these two arms.

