5.7.3. Analysis of Exploratory Vaccine Response Variables

Exploratory vaccine response variables will be analyzed in a similar manner as described for the secondary vaccine response variables.

Accompanying descriptive analyses will be provided to all (primary/secondary/exploratory) vaccine response variables.

The distribution of endpoint variables will be checked to ensure ANCOVA type analyses are appropriate. If such modeling is deemed not appropriate, only raw data descriptions will be provided.

On limited numbers of samples, an exploratory analysis will be performed with data from a second neutralization assay that will be summarized in a separate report.

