6.1. Definition of Baseline

Unless otherwise specified, the baseline assessment for all measurements will be the latest available valid measurement taken prior to the administration of the first dose of Moderna mRNA-1273 vaccine or REGN10933+REGN10987 (as applicable and whichever occurs first).

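### SAP 5.7.2 and 5.7.3 adjust binding-antibody and T/B-cell responses for age but not for the subject's own day-1 value, which costs some precision, mainly for the T/B-cell variables

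*SAP*

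**What the plan says.** **Model.** For the secondary variables, SAP 5.7.2 says: "Secondary vaccine response variables will also be analyzed using an ANCOVA model with treatment group as a fixed effect and age as a covariate". SAP 5.7.3 adds: "Exploratory vaccine response variables will be analyzed in a similar manner as described for the secondary vaccine response variables". Protocol 11.4.3 likewise names only age ("An analysis of covariance (ANCOVA) model with treatment group as a fixed effect and age as a covariate will be fit to the data"), and Protocol 11.4.4 treats the secondary endpoints similarly. No section puts the baseline value of the response into a model.

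**Variables.** SAP 4.5.2 lists, for binding antibody, "Absolute values, change from baseline, and percentage change from baseline in concentrations of vaccine-induced antibodies to the following SARS-CoV-2 antigens over time". SAP 4.5.3 lists, for T cells, "Absolute percentages, change, and percentage change from baseline of blood-derived memory T cell responses specific to SARS-CoV-2 viral peptides over time", and defines the B-cell variable in the same way. After describing the model, SAP 5.7.2 adds: "Numerical summaries of observed value, change from baseline, and percentage change from baseline will also be tabulated".

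**Baseline.** For vaccine-response variables SAP 5.7 says "baseline is defined as the last available value prior to the first dose of Moderna mRNA-1273 vaccine". SAP 6.1 gives the general rule: "Unless otherwise specified, the baseline assessment for all measurements will be the latest available valid measurement taken prior to the administration of the first dose". There, the dose meant is that of vaccine or study drug, depending on which is given earlier.

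**Samples.** The Schedules of Events (Protocol Tables 3 to 5) place serology serum and whole blood for PBMCs at the day-1 pre-dose visit in all arms. Footnote 1 requires sampling before any product is given.

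**The concern.** A response measured before and after vaccination usually carries information in its first reading. Leaving that reading out of an absolute-value model discards it. Subtracting it without adjusting for it (a change score with age only) brings its full noise into the contrast. Either way, the interval for a drug arm against pooled vaccine alone can be wider than necessary. The study plans no hypothesis tests, so estimates and intervals are its product.

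There is also a question of consistency. If absolute value and change are both modelled with age only, each variable has two contrasts, and they differ by the baseline difference between the groups. SAP 5.7 adds to this. In arms 1, 2, 3, 7 and 8 the last sample before the first vaccine dose is the day-15 sample, taken about 14 days after the study drug. Any effect of the drug on that reading, such as incomplete anti-idiotype blocking in the binding assay, would then be subtracted out of the change score.

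The T/B-cell variables are the most exposed. Per-protocol criteria 1 and 8 (SAP 3.1) remove subjects with positive central serology or a baseline neutralizing titer above the LLOQ. Neither criterion acts on T/B-cell percentages.

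**Working it through.** **Inputs from the documents.** 30 subjects per drug arm and 46 pooled vaccine-alone subjects (SAP 2.2); SD 0.30 log10 (Protocol 11.2), which is an ID50 figure used here only as a scale; 95% two-sided intervals.

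**Assumed inputs, not in the documents.** r = baseline SD / follow-up SD; ρ = correlation between baseline and follow-up. Ranges are shown.

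**Step 1. Reproduce the plan's figure.** √(1/30 + 1/46) = 0.235. Residual df = 286 − 9 groups − 1 for age = 276. The half-width t × 0.30 × 0.235 is 0.139, which agrees with the stated 0.14. The plan gives no precision figure for binding-antibody or T/B-cell variables.

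**Step 2. Relative variance of the contrast.**
- Age-only, absolute value: 1
- Age-only, change: 1 + r² − 2ρr
- Baseline-adjusted, either form: 1 − ρ²

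Half-widths on the 0.30 scale:

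| r | ρ | Absolute, age only | Change, age only | Baseline-adjusted |
|---|---|---|---|---|
| 1 | 0 | 0.139 | 0.196 | 0.139 |
| 1 | 0.2 | 0.139 | 0.175 | 0.136 |
| 1 | 0.5 | 0.139 | 0.139 | 0.120 |
| 1 | 0.7 | 0.139 | 0.107 | 0.099 |
| 0.5 | 0 | 0.139 | 0.155 | 0.139 |
| 0.5 | 0.5 | 0.139 | 0.120 | 0.120 |
| 0 (all at one floor value) | any | 0.139 | 0.139 | 0.139 |

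Ratios of age-only to adjusted half-width:
- Absolute, 1/√(1 − ρ²): 1.00, 1.05, 1.15, 1.40 at ρ = 0, 0.3, 0.5, 0.7.
- Change at r = 1, √(2/(1 + ρ)): 1.41, 1.24, 1.15, 1.08 at the same ρ.
- Change at r = 0.5, √((1.25 − ρ)/(1 − ρ²)): 1.12, 1.02, 1.00 at ρ = 0, 0.3, 0.5.

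**Step 3. Disagreement between absolute and change contrasts.** With age-only models, the change contrast minus the absolute contrast equals minus the age-adjusted baseline difference. By chance alone its 95% range is ±1.96 × 0.235 = ±0.46 baseline SDs. On the 0.30 scale that is ±0.138 log10 (1.37-fold) at r = 1, ±0.069 (1.17-fold) at r = 0.5, ±0.014 (1.03-fold) at r = 0.1, and zero at a common floor. In 4,000 simulated trials at r = 1, ρ = 0.5 and no true effect, the SD of the disagreement was 0.070 (formula: 0.235 × 0.30 = 0.070), and the two contrasts had opposite signs in 33%. With baseline in the model they agreed to within 1e-14.

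**Step 4. The same baseline must serve both purposes.** The agreement in step 3 needs one value as both covariate and subtracted value. Suppose day 1 is the covariate but day 15 is subtracted, with equal SDs, an assumed day-1 to day-15 correlation of 0.7, and all 46 controls treated as measured on day 15. The remaining disagreement has SD 0.235 × √(1 − 0.49) = 0.17 baseline SDs. It would be somewhat smaller in practice, because arms 6b and 6d (15 + 8 = 23 of the 46) have day 1 as baseline anyway. Any drug effect on the day-15 reading would add to it.

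**The case against.** **Binding-antibody baselines are probably near a floor.** Subjects must be seronegative, RT-PCR-negative and unvaccinated; the per-protocol set drops central-serology positives and titers above the LLOQ; values below the LLOQ become half the LLOQ. This largely stands, so for the variables named in SAP 5.7.2 itself the gain is probably small.

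**Change may only be tabulated.** SAP 5.7.2 describes log modelling of concentrations and then numerical summaries of change, and a negative raw change cannot be logged. SAP 4.5.2, however, lists change among the variables that the model applies to. Both readings are open. If change is only tabulated, the change ratios and the two competing contrasts fall away; the precision point for absolute values remains.

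**The weight is limited.** T/B-cell variables are exploratory, some such analyses may not reach the study report (Protocol 9.2.3), and SAP 5.7.3 allows description only if the model does not suit the data. This stands.

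**The age-only model is the protocol's, and the trial is open-label with an interim analysis of waves 1 and 2 already recorded in Amendment 5.** A change of model therefore needs a stated reason. The reason here comes from the design, not from results.

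Three stronger readings may tempt a reader. The first is that the age-only contrasts are biased. Within a wave, randomization protects them and only precision is lost; pooling controls across waves is a separate question. The second is that SAP 5.7 and 6.1 contradict each other. SAP 6.1 gives way where another rule is specified, so they diverge without conflict. The third is that the primary result is at risk. It is an absolute titer, and criterion 8 removes subjects with a baseline titer above the LLOQ.

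**Conclusion.** The point holds as a matter of precision and clarity. The day-1 pre-product value is collected in every arm and used in no model. Under assumed r and ρ, age-only half-widths are 1.00 to 1.40 times the adjusted ones for absolute values (ρ 0 to 0.7) and 1.00 to 1.41 times for change (r 0.5 to 1, ρ 0 to 0.5). There is no gain if all baselines share one floor value. The benefit should fall mainly on the exploratory T/B-cell variables.

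Disagreement between absolute and change contrasts is conditional on change being modelled. If it is, the disagreement can be due to chance in any arm, and systematic in arms 1, 2, 3, 7 and 8 if the study drug affects the day-15 reading. The documents give no baseline SD or correlation, so the actual size cannot be fixed from them.

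**What to change.** In SAP 5.7, 5.7.2 and 5.7.3, for binding-antibody and T/B-cell variables only:

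1. Define baseline as the last value before either product, meaning the day-1 pre-dose sample in every arm. This follows SAP 6.1 for the drug arms. Name the day explicitly, because in arms 6a and 6c, which receive no drug, a literal reading of 6.1 gives day 15.
2. Use that same value, on the analysis scale, as the covariate and as the value subtracted in change. The day-15 value in arms 1, 2, 3, 7 and 8 follows randomization and drug, and should serve as neither.
3. State that the modelled result is one baseline-adjusted contrast per variable and post-vaccine visit. Keep change and percentage change as descriptive tabulations, so that the protocol-listed endpoints are still reported.
4. Set a rule, written without reference to arm results, for omitting the covariate where baseline has essentially no spread, and a simple rule for missing day-1 values.
5. Record the departure from the protocol's age-only model, with its reason, in SAP 1.2.5.

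The cost is one degree of freedom and a documented departure from the protocol model. No new data are needed, and the primary ID50 model stays as it is.
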